### Per Protocol Set Analysis

Sensitivity analyses based on the PPS will be performed using the same approach as specified for the primary analysis in the beginning of this section. Values of the stratifying variables utilized for analysis on the PPS will be those captured in the EDC system.

### USM Analysis Set

WOMAC Pain and Physical function will be summarized descriptively based on the USM Analysis set. No sensitivity analysis will be conducted using the USM analysis set.

#### **5.7.2. Subgroup analysis:**

Descriptive analyses by treatment group will be performed on both raw and change from baseline values for each visit for the WOMAC pain subscale score and physical function subscale scores to summarize the treatment effects across subpopulations defined by the following baseline characteristics:

- K-L category [2 to 3, or 4]
- Index joint [Knee, Hip]
- Region [North America, Europe, Other]
- Age group [ $< 65$ , 65-74,  $\geq 75$  ]
- Sex [Male, Female]
- Weight group [ $< \text{Median}$ ,  $\geq \text{Median}$ ]
- BMI group [ $\leq \text{Median}$ ,  $> \text{Median}$ ]
- Flare status [Flare, non-flare] : Flare patients are defined as patients who experience a  $\geq 1$  point increase in WOMAC pain scores from the Screening to the Baseline Visit

An MMRM model analogous to that used for the primary analysis will be constructed, also including terms for subgroup and subgroup-by-treatment, subgroup-by-visit and subgroup-by-treatment-by-visit interactions as fixed effects. Multiple imputation will not be performed for the subgroup analyses. In addition to the actual change from baseline values, their LS means, differences of LS Means between treatment groups and corresponding 95% CIs within each subgroup at each visit will be presented. The p-value corresponding to the overall effect of the overall subgroup-by-treatment interaction will be supplied. Forest plots for the subgroup analysis will be provided.

#### **5.7.3. Analysis of Secondary Efficacy Variables**

The following secondary hypotheses specified in the study protocol that will be tested:

- H2: There is no treatment difference between fasinumab 1 mg Q4W and placebo in the Patient Global Assessment score at week 24 versus there is treatment difference in Patient Global Assessment score at week 24
- H3: There is no treatment difference between fasinumab 1 mg Q4W and placebo in the proportion of patients with  $\geq 30\%$  improvement in the WOMAC pain subscale

scores at week 24 versus there is treatment difference in proportion of patients with  $\geq 30\%$  improvement in WOMAC pain at week 24

- H4: There is no treatment difference between fasinumab 1 mg Q4W and NSAIDs in the WOMAC pain subscale scores at week 24 versus there is treatment difference in WOMAC pain subscale scores at week 24
- H5: There is no treatment difference between fasinumab 1 mg Q4W and NSAIDs in the WOMAC physical function subscale scores at week 24 versus there is treatment difference in WOMAC physical function subscale scores at week 24
- H6: There is no treatment difference between fasinumab 1 mg Q4W and NSAIDs in the Patient Global Assessment score at week 24 versus there is treatment difference in Patient Global Assessment score at week 24

The hypotheses H4 and H5 can be tested within the same analysis method used to test H1 as described in Section 5.7.1.

To test H2 and H6, a method analogous to that used to test H1 in Section 5.7.1 can be utilized, replacing the respective WOMAC subscale score with the PGA score. The multiple imputation algorithm will be modified to truncate values outside the range of the PGA score (0-5) in a manner similar to the primary analysis.

To test H3 the Cochran Mantel Haenszel (CMH) approach stratified by the randomization strata (K-L category [2 to 3, or 4], index joint [knee, hip], and geographical region[Other, Europe, North America]) will be used with missing data considered as non-response.

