### **8.2.2.2. Patient Global Assessment of Osteoarthritis**

The Patient Global Assessment of OA is a patient-rated assessment of their current disease state on a 5-point Likert scale (1 = very good; 2 = good; 3 = fair; 4 = poor; and 5 = very poor). Patients will complete the assessment scale at the time points indicated in [Table 1](#).

A copy of the assessment is provided in the study reference manual.

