## 10.2. Justification of Sample Size

Assuming a 2-sided alpha level 0.05 and a 20% dropout rate up to week 24, an enrollment of 600 patients in the fasinumab 1 mg Q4W group and 300 patients in the placebo group will provide at least 99% power to detect an effect size of 0.46 in the WOMAC pain and physical function subscale scores (ie, absolute treatment difference of 1.1 between fasinumab and placebo with a SD of 2.4). The assumed treatment difference and standard deviation (SD) are based on results from study R475-PN-1227. The sample size will provide 99% power to detect an effect size of 0.36 in PGA (ie, absolute treatment difference of 0.4 with a SD of 1.1, R475-PN-1227).

Assuming a 2-sided alpha level 0.05 and a 20% dropout rate up to week 24, an enrollment of 600 patients in the fasinumab 1 mg Q4W group and the pooled NSAIDs group will provide approximately 92% power to detect an effect size of 0.22 in the WOMAC pain subscale (ie, absolute treatment difference of 0.51 with a SD of 2.3, [Schnitzer 2015]). The sample size will provide 95% power to detect an effect size of 0.24 in WOMAC physical function subscale (ie, absolute treatment difference of 0.50 with a SD of 2.1, [Schnitzer 2015]), and 79% power to detect an effect size of 0.18 in PGA (ie, absolute treatment difference of 0.18 with a SD of 1.0 [Ekman 2014]).

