- Step 1: The monotone missing pattern is induced by Markov Chain Monte Carlo (MCMC) method in MI procedure using seed number 4751688. Any score imputed outside the range of the WOMAC subscale score of 0-10 will be truncated to the nearest permissible value on the WOMAC scale according to the following algorithm:
  - If the imputed score  $> 10$ , then the final imputed score will be 10.
  - If the imputed score  $< 0$ , then the final imputed score will be 0.
- Step 2: The missing WOMAC subscale scores at visits subsequent to treatment discontinuation will be imputed using the regression method for the monotone pattern with seed number 4751688 and adjustment for covariates including treatment groups, randomization strata (K-L category [2 to 3, or 4], index joint [knee, hip], and

geographical region [Other, Europe, North America]), baseline WOMAC subscale score and all WOMAC subscale scores at preceding visits. Scores that are imputed outside the range of the WOMAC subscale will be truncated in the same manner as in step 1. As the regression method imputes missing data sequentially by visits, the truncation will be implemented after each visit iteration.

- Step 3: For patients who permanently discontinued study treatment due to lack of efficacy, death or AEs, the initially missing and now imputed WOMAC subscale scores at visits subsequent to treatment discontinuation will be adjusted to be centered at the mean baseline value for that treatment group, i.e., imputed score = initial imputed score under MAR – (mean change from baseline subscale score at the post-baseline time point for the treatment group based on patients on treatment with non-missing data at that time point). Scores that are adjusted to outside the range of the WOMAC subscale will be truncated in the same manner as in step 1.

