#### 5.7.4. Adjustment for Multiple Comparison

To control the overall Type I Error of the clinical trial at 5%, the sequentially rejective multiple test procedure (Bretz 2009) will be applied. Hypothesis H1 will be tested at  $\alpha_0 = 0.05$ . As it is a hypothesis test concerning the co-primary endpoints, the hypothesis will be rejected if the following is met:

- The hypothesis of no treatment difference between fasinumab 1 mg Q4W and placebo in WOMAC pain subscale at week 24 is rejected  $\alpha_0 = 0.05$

AND

- The hypothesis of no treatment difference between fasinumab 1 mg Q4W and placebo in WOMAC physical function subscale at week 24 between fasinumab and placebo is rejected  $\alpha_0 = 0.05$

If a hypothesis is rejected, the alpha level for that hypothesis will be reallocated to other hypothesis according to the graph. The graph will be updated according to the pre-specified algorithm, as described by Bretz 2009. The rest of the hypotheses will be tested at the updated alpha level based on the updated graph. The testing will stop when no hypothesis can be rejected at any step.

If the primary analysis of efficacy is successful, secondary endpoints will be tested according to hierarchical testing strategy based on the following order:

H3 → H2 → H4 → H5 → H6

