### 10.5. OMERACT – OARSI RESPONDER CRITERIA

Note that the criteria in the diagram above are based on standardized scores between 0 and 100. For this study, WOMAC pain and physical function score are between 0 and 10, so the absolute change required for response is the required change in the diagram above divided by 10; PGA is 1, 2, 3, 4 or 5, so the absolute change required for response is at least 1 point.

Signature Page for VV-RIM-00105092 v1.0

ESig Approval	[Redacted] 000
---------------	----------------

ESig Approval	[Redacted] 000
---------------	----------------

ESig Approval	[Redacted] 20 21:23:06 GMT+0000
---------------	---------------------------------

ESig Approval	[Redacted] 000
---------------	----------------

ESig Approval	[Redacted] -2020 11:18:46 GMT+0000
---------------	------------------------------------

ESig Approval	[Redacted] -2020 12:11:47 GMT+0000
---------------	------------------------------------

Signature Page for VV-RIM-00105092 v1.0 Approved

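### SAP 5.7.3 truncates imputed PGA scores to 0-5, but PGA runs from 1 to 5, so the lower bound is wrong (minor)

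*SAP*

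**What the plan says.** SAP 5.7.3 tests H2 (fasinumab against placebo) and H6 (fasinumab against pooled NSAIDs) on PGA with the method of SAP 5.7.1, substituting PGA for the WOMAC score. On bounds it states: "The multiple imputation algorithm will be modified to truncate values outside the range of the PGA score (0-5", and it says to do this in the same way as the primary analysis.

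In the primary analysis (SAP 5.7.1, Step 1), an imputed score outside the scale "will be truncated to the nearest permissible value on the WOMAC scale according to the following algorithm". WOMAC runs from 0 to 10, so for a negative draw "then the final imputed score will be 0". In Step 2, "the truncation will be implemented after each visit iteration". Step 3 truncates again after its adjustment.

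The scale itself is given in two places. Protocol 8.2.2.2 describes a "5-point Likert scale (1 = very good; 2 = good; 3 = fair; 4 = poor; and 5 = very poor". SAP 10.5 says "PGA is 1, 2, 3, 4 or 5, so the absolute change required for response is at least 1 point".

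**The concern.** The SAP prints a lower bound of 0 for a scale whose lowest score is 1. A program written to that bound keeps imputed scores between 0 and 1 and sets negative draws to 0. No patient can record either kind of value. Step 2 conditions each imputation on scores at earlier visits, so an impossible value can also feed later ones.

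H2 and H6 are alpha-controlled. SAP 5.7.4 says "secondary endpoints will be tested according to hierarchical testing strategy based on the following order": H3, H2, H4, H5, H6. H2 therefore gates three further tests, and H6 is planned with modest power. The question is whether the wrong bound could move either test.

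**Working it through.** **The scale, side by side**

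| Place | PGA range |
|---|---|
| Protocol 8.2.2.2 | 1 to 5, each score labelled |
| SAP 10.5 | 1, 2, 3, 4 or 5 (no labels) |
| SAP 5.7.3 | 0-5 |

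The upper bound agrees everywhere. The lower bound in SAP 5.7.3 agrees with neither of the other places.

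**The plan's own PGA power**

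Inputs from Protocol 10.2 and SAP 2.2: two-sided alpha 0.05, 20% dropout; H2 600 against 300, difference 0.4, SD 1.1; H6 600 against 600, difference 0.18, SD 1.0. After dropout the group sizes are 480 and 240 (H2), and 480 and 480 (H6). Power = Φ(difference/SE − 1.96).

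- H2: SE = 1.1 × √(1/480 + 1/240) = 0.0870; 0.4/0.0870 = 4.60; power 99.6% (stated 99%).
- H6: SE = 1.0 × √(1/480 + 1/480) = 0.0645; 0.18/0.0645 = 2.79; power 79.6%. Protocol 10.2 states "79% power to detect an effect size of 0.18 in PGA".

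Both reproduce. Neither uses the truncation range.

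**Effect of the floor**

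Assumptions, because the documents give no PGA means:
- Fasinumab week 24 mean 2.5, with a range of 2.2 to 2.8; the comparator mean is higher by the planned difference.
- Normal imputed draws with SD 1.0 to 1.1. The plan's SDs are for a change-from-baseline endpoint; using them for the week 24 score is itself an assumption.
- All of the 20% dropout imputed under MAR, which is the upper end.

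Share of fasinumab draws below 1 at mean 2.5: Φ((1 − 2.5)/1.0) = 6.7%; at SD 1.1, 8.6%. The range over means 2.2 to 2.8 is 3.6% to 13.8%. Of the 120 imputed patients (20% of 600), that is 8 to 10 per data set (4 to 17 over the range). Draws below 0 are 0.6% to 1.2%.

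The mean of a normal draw clipped to [a, b], with A = (a − μ)/σ and B = (b − μ)/σ, is

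aΦ(A) + b(1 − Φ(B)) + μ(Φ(B) − Φ(A)) − σ(φ(B) − φ(A)).

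Difference among imputed scores only, SD 1.0:

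| Test | Assumed means | Unclipped | Floor 0 | Floor 1 |
|---|---|---|---|---|
| H2 | 2.5 and 2.9 | 0.400 | 0.394 | 0.377 |
| H6 | 2.5 and 2.68 | 0.180 | 0.178 | 0.168 |

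The overall difference is 0.8 × planned difference + 0.2 × imputed difference. For H6 at SD 1.0:
- Floor 0: 0.8 × 0.18 + 0.2 × 0.1777 = 0.1795
- Floor 1: 0.8 × 0.18 + 0.2 × 0.1684 = 0.1777

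Power here uses the variance of the 80/20 mixture, which falls slightly when draws are clipped at 1.

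| Test, SD | Difference, floor 0 → 1 | Power, floor 0 → 1 |
|---|---|---|
| H2, 1.0 | 0.3988 → 0.3955 | falls 0.003 points |
| H2, 1.1 | 0.3979 → 0.3935 | falls 0.015 points |
| H6, 1.0 | 0.1795 → 0.1777 | 79.62% → 79.49% |
| H6, 1.1 | 0.1791 → 0.1768 | 71.70% → 71.50% |

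Over means 2.2 to 2.8, the difference shrinks by 0.002 to 0.007 (H2) or 0.001 to 0.004 (H6). Power falls by at most 0.03 points (H2) or by 0.06 to 0.39 points (H6).

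**Step 3**

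Patients who stop for lack of efficacy, adverse events or death are re-centred at the baseline mean. At an assumed baseline mean of 3.5, only 0.6% to 1.2% of such values fall below 1, so the floor matters mainly for scores left under MAR and for intermittent gaps.

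**The case against.** The strongest objection is that this is a one-digit slip with no consequence. The operative instruction is to truncate to the range of the PGA score; the figure in brackets misstates that range, and a programmer who checked SAP 10.5 or the protocol would use 1 to 5. Observed scores are untouched. This supports the minor rating, but it does not make the printed bound right, and the printed bound is what a programmer would normally code.

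A second objection is that the size is known less precisely than two-decimal power figures suggest. This stands. With a fasinumab mean of 1.8, 21% to 23% of draws fall below 1, the differences shrink by up to 0.012 (H2) and 0.006 (H6), and H6 power falls by 0.68 to 0.84 points. If the SD is held at 1.0 instead of falling with clipping, the H6 loss is 0.82 points at mean 2.5 and 2.6 points at mean 1.8. Treating 480 per arm as the effective size is also only a rough stand-in for the repeated-measures model with Rubin's rules.

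Third, the direction depends on the comparator. Against the unclipped MAR mean, the 0 floor does not inflate the fasinumab effect. Against the correct floor of 1, it leaves a slightly larger difference in fasinumab's favour, because low PGA is good. The case for the change is correctness, not bias.

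Non-integer imputed values within the range are not a fault: the primary rule bounds scores and does not round them.

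**Conclusion.** The concern holds, as a minor error. The lower bound in SAP 5.7.3 contradicts the instrument as defined in Protocol 8.2.2.2 and SAP 10.5, and it departs from the nearest-permissible-value rule that SAP 5.7.3 says it follows. The upper bound, the observed PGA scores and the WOMAC truncation are correct.

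The numerical effect is very small: at a fasinumab mean of 2.5, about 1% of the planned difference for either test, and about 3% in the least favourable case examined (mean 1.8). These sizes rest on assumed PGA means, normal draws, the planning SDs and a 20% imputed share. No conclusion on H2 or H6 is expected to turn on it.

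**What to change.** Before database lock, change the PGA range in SAP 5.7.3 from 0-5 to 1-5. An imputed PGA below 1 is then set to 1, and one above 5 is set to 5, at each point where the primary algorithm truncates: Step 1, each visit iteration of Step 2, and Step 3. The cost is one number in the SAP and one constant in the program. Nothing in the design, the data collection or the other analyses changes.

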#### 5.7.4. Adjustment for Multiple Comparison

To control the overall Type I Error of the clinical trial at 5%, the sequentially rejective multiple test procedure (Bretz 2009) will be applied. Hypothesis H1 will be tested at  $\alpha_0 = 0.05$ . As it is a hypothesis test concerning the co-primary endpoints, the hypothesis will be rejected if the following is met:

- The hypothesis of no treatment difference between fasinumab 1 mg Q4W and placebo in WOMAC pain subscale at week 24 is rejected  $\alpha_0 = 0.05$

AND

- The hypothesis of no treatment difference between fasinumab 1 mg Q4W and placebo in WOMAC physical function subscale at week 24 between fasinumab and placebo is rejected  $\alpha_0 = 0.05$

If a hypothesis is rejected, the alpha level for that hypothesis will be reallocated to other hypothesis according to the graph. The graph will be updated according to the pre-specified algorithm, as described by Bretz 2009. The rest of the hypotheses will be tested at the updated alpha level based on the updated graph. The testing will stop when no hypothesis can be rejected at any step.

If the primary analysis of efficacy is successful, secondary endpoints will be tested according to hierarchical testing strategy based on the following order:

H3 → H2 → H4 → H5 → H6

### 5.7.5. Analysis of Other Efficacy Variables

#### Responder Analysis

The percentage of patients who are responders based on WOMAC pain and physical function subscale scores defined by at least a 30% reduction and at least a 50%, 70% reduction from baseline to each post-baseline week will be summarized and plotted by treatment group. The percentage of patients who are responders based on the Osteoarthritis Research Society International Standing Committee for Clinical Trials Response Criterial Initiative and THE Outcome Measure in Rheumatology (OMERACT -OARSI) responder criteria will be summarized and plotted by treatment group. Cochran -Mantel-Haenszel (CMH) test, stratified by the randomization strata will be applied for the responder analysis. Missing data is considered as non-response in this analysis.

Cumulative distribution of percent change from baseline to Week 24 in the WOMAC pain and physical function scores will be presented by treatment group. The cumulative distribution plot displays a continuous plot of the percent change from baseline on the X-axis and the percent of patients experiencing that change on the Y-axis. Different responder definitions can be identified along the distribution curve.

#### Walking Index Joint Pain Numeric Rating Score (NRS)

For the analysis of average weekly walking index joint pain using the NRS pain scale, baseline is defined as the average of the non-missing values during 7 days prior to taking study drug. For each week, the average of the non-missing values during the 7 days on or prior to that week will be used. If all values are missing for the 7 days, the value for that week is set to missing.

The MMRM model will include the randomization strata (K-L category [2-3 vs. 4], index joint [hip or knee] and geographic region), treatment, week (weeks 1, 2, ..., 24), treatment-by-week interaction as fixed effects, and baseline average NRS value as a covariate. The least-squares (LS) means for the mean change from baseline to each week, as well as the LS mean differences between fasinumab doses and placebo, with their corresponding standard errors (SEs), p-values and associated 95% confidence intervals, will be provided from the MMRM. If the model does not converge using unstructured covariance matrix, an autoregressive 1 covariance structure will be used.

#### Rescue Medications

The number (and percentage) of patients using rescue medication, during the Pre-Treatment Period will be summarized by treatment group and overall based on the SAF. Similar analysis will be performed for the On-Treatment Period based on the SAF.

For patients taking rescue medication, descriptive statistics of the number of days patients took rescue medications will be presented by treatment group during the On-Treatment Period based on the SAF.

For patients taking rescue medication, weekly average usage of rescue medication (measured in mg) is calculated as follows:

$$= \frac{\text{Total amount of rescue medication used in the specified week (in mg)}}{\text{\# of diary entries in the specified week}}$$

Descriptive statistics of the weekly average usage of rescue medications for OA pain will be presented by treatment group based on the SAF.

#### Average WOMAC pain and physical function Score across Week 12 to Week 24

Change in WOMAC pain and physical function subscale scores from baseline to the average score across Weeks 12, 16, 20 and 24 will be analyzed using the same multiple imputation method used to analyze the primary efficacy endpoints in Section 5.7.1. However, the analysis model for the average of the WOMAC subscale scores across multiple visits will instead be an ANCOVA model with terms for baseline WOMAC subscale score, randomization strata (K-L category [2 to 3, or 4], index joint [knee, hip], and geographical region [Europe, North America, Other]) and treatment.

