**8.1.1. Footnotes for the Schedule of Events Table**

1. Patients who discontinue study medication before week 24 will be encouraged to follow the visit schedule through the remainder of the study. If a patient chooses to end study participation, he or she will be asked to return to the clinic as soon as possible for an early termination visit. Imaging assessments need to be repeated if it has been >30 days since the joints were last imaged. If it has been ≤30 days since imaging assessments were completed, imaging assessments may be completed at the discretion of the investigator.
2. HIV and/or hepatitis testing will be performed on a country-by-country basis, according to local guidelines if required by regulatory authorities or ethics boards
3. Only for patients who provide written informed consent for the optional genomics sub-study. The sample should be collected at the day 1 (baseline/randomization) visit, but may be collected at any visit during the study after a patient has been randomized.
4. At the screening and pre-randomization visits, study staff will review the “Participating in a Research Study: What You Need to Know” brochure and the “Reporting Your Pain” brochure with patients to ensure they understand what a clinical study is and how to report their pain accurately. At subsequent visits, patients will be asked to review the “Reporting Your Pain” brochure themselves. At any time during the conduct of the study, patients may require retraining by study staff.
5. Subcutaneous study drug administration will be the last procedure at each dosing visit, and will be done after all laboratory, PK, ADA and research samples have been collected and all study assessments performed. Patients will be observed in the clinic for approximately 1 hour after SC study drug is administered.
6. Use of study-provided rescue medication will be recorded daily using diaries. Acetaminophen/paracetamol use will be reported from pre-randomization visit to week 24.
7. Patients will complete the WOMAC pain subscale for both hips and knees at the screening visit. Then, the WOMAC Full Survey will be completed only for the index joint at subsequent visits.
8. Walking index joint pain NRS score will be recorded by the patient each day using their diary, starting during the pre-randomization period through week 24. Walking index joint pain NRS score will be recorded by the patient at the site at the week 24 visit.

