### **4.5.3. Exploratory Variable(s)**

The exploratory endpoints in the study are

- Change from baseline to week 24 in patient-reported outcome measures in patients with pain due to OA of the knee or hip treated for up to 24 weeks with fasinumab compared to placebo
- Change from baseline to week 24 in patient-reported outcome measures in patients with pain due to OA of the knee or hip treated for up to 24 weeks with fasinumab compared to NSAIDs (pooled celecoxib and diclofenac arms)

- The proportion of patients taking rescue medication, number of days on rescue medication, and weekly average use of rescue medication from baseline to week 24 in patients with pain due to OA of the knee or hip treated for up to 24 weeks with fasinumab compared to placebo
- The proportion of patients taking rescue medication, number of days on rescue medication, and weekly average use of rescue medication from baseline to week 24 in patients with pain due to OA of the knee or hip treated for up to 24 weeks with fasinumab compared to NSAIDs (pooled celecoxib and diclofenac arms)
- Change in WOMAC pain subscale scores from baseline to the average score across Weeks 12, 16, 20 and 24 with fasinumab compared to placebo
- Change in WOMAC physical function subscale from baseline to the average score across Weeks 12, 16, 20 and 24 with fasinumab compared to placebo

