## 5. STATISTICAL METHODS

For continuous variables, descriptive statistics will include the following: the number of patients reflected in the calculation (n), mean, median, standard deviation, minimum & maximum and 1st & 3rd quartiles (Q1 & Q3).

For categorical or ordinal data, frequencies and percentages will be displayed for each category.

**Period of Observation** - Unless otherwise stated, analysis of all safety and non-safety variables captured at multiple visits will be analyzed by the following observation periods:

- The Pre-Treatment Period is defined as the time from signing the ICF to before the first dose of study drug.
- The On-Treatment Period is defined as the time from the first dose of study drug up to 28 days after the last dose of study drug.
- The Follow-Up/Post-Treatment Period is defined from the end of the On-Treatment Period to the date of the follow-up clinic visit (Week 44 visit) or early termination date.

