## **5.4. Prohibited Medications**

### Prohibited Medications

Summaries of prohibited medications will present patient counts (and percentages) for all prohibited medications, dictionary coded by WHO, by decreasing frequency of the overall group incidence (or fasinumab 1mg Q4W group incidence in tables where the overall is not presented) of ATC followed by ATC level 2, ATC level 4 and preferred term. In case of equal frequency across anatomic or therapeutic categories, alphabetical order will be used. Patients will be counted once in each ATC category (anatomic or therapeutic) linked to the medication, but may be counted several times for the same medication.

Number and percentage of patients with prohibited medications will be descriptively summarized by treatment group, and combined fasinumab group based on the SAF.

The number of patients with prohibited NSAID use during the on-treatment period will be summarized by treatment group. Total prohibited NSAIDs-use days during the treatment period and follow-up (before AA for patients with AA) will be summarized by treatment group. Additionally, days from last study drug dose to first NSAID dose will be summarized.

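### Two of the three exploratory rescue measures in SAP 5.7.5 (any use, number of rescue days) have no observation-time denominator, so they shift with unequal early stopping as well as with rescue need

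*SAP*

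**What the plan says.** SAP 4.5.3 lists the rescue endpoints, against placebo and against pooled NSAIDs, as "The proportion of patients taking rescue medication, number of days on rescue medication, and weekly average use of rescue medication from baseline to week 24". SAP 5.7.5 (Rescue Medications) sets out how each is summarised:

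- **Any use.** "The number (and percentage) of patients using rescue medication, during the Pre-Treatment Period will be summarized by treatment group", followed by "Similar analysis will be performed for the On-Treatment Period based on the SAF". The denominator is patients, with no allowance for days observed.
- **Days of use.** Among patients who took rescue, "descriptive statistics of the number of days patients took rescue medications will be presented by treatment group during the On-Treatment Period". This is a raw count.
- **Weekly amount.** Among the same patients, "weekly average usage of rescue medication (measured in mg) is calculated as follows": total mg in the week divided by the number of diary entries in that week.

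The counting window, set in SAP 5, is tied to dosing: "The On-Treatment Period is defined as the time from the first dose of study drug up to 28 days after the last dose of study" (treatment). SAP 2.1 places the last Q4W dose at week 20 and gives the washout as 7 to 10 days. On the diary, Protocol 8.1.1 (footnote 6) says: "Acetaminophen/paracetamol use will be reported from pre-randomization visit to week 24". Protocol 7.7.2 sends acetaminophen taken during screening to the concomitant medication record instead.

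A related count is in SAP 5.4: "Total prohibited NSAIDs-use days during the treatment period and follow-up (before AA for patients with AA) will be summarized by treatment group".

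**The concern.** A count of days with an event is interpretable between arms only if the arms were watched for similar lengths of time. Here the window closes 28 days after the last dose, so stopping treatment shortens it. SAP 5.7.1 separates discontinuation for lack of efficacy, adverse events or death from other reasons. It cannot be assumed that stopping will be equally frequent, or equally early, on fasinumab, NSAID and placebo. If one arm loses more patients early, its mean number of rescue days falls even when daily use is the same. A reader could take that for lower rescue need. Any use has the same dependence in a weaker form, because the chance of at least one use rises with the number of days observed.

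What is at stake is the reading of two of the three endpoints that serve the exploratory rescue-medication objective (SAP 1.2.3). No tested hypothesis depends on them.

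**Working it through.** The documents state no rescue rate, so there is no figure of the plan to reproduce. The daily-use and arm-specific stopping rates below are assumptions. From the documents come the windows and the overall 20% dropout by week 24 (SAP 2.2).

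**1. Window length.** The last injection is at nominal day 141. A completer's On-Treatment Period is 141 − 1 + 28 = 168 days. A patient with one injection has 28 days. The ratio is 168/28 = 6.

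**2. Mean day count.** With daily use p, a fraction q stopping early, and stoppers observed L days on average, mean days = p × [(1 − q) × 168 + q × L].

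Take p = 0.4 in both arms, with stopping spread equally over injections 1 to 5. Then L = mean(28, 56, 84, 112, 140) = 84.

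- q = 15%: 0.85 × 168 + 0.15 × 84 = 155.4 days observed; × 0.4 = 62.2 rescue days.
- q = 30%: 0.70 × 168 + 0.30 × 84 = 142.8 days observed; × 0.4 = 57.1 rescue days.

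The difference is about 5 days with identical daily use.

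**3. Range over other assumptions** (same formula)

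| Daily use, arm A / B | Stopping, A / B | L (days) | Mean rescue days, A / B |
|---|---|---|---|
| 0.30 / 0.30 | 10% / 30% | 28 | 46.2 / 37.8 |
| 0.30 / 0.30 | 10% / 30% | 84 | 47.9 / 42.8 |
| 0.30 / 0.30 | 10% / 30% | 140 | 49.6 / 47.9 |
| 0.30 / 0.30 | 20% / 20% | 28 | 42.0 / 42.0 |
| 0.30 / 0.33 | 10% / 30% | 28 | 46.2 / 41.6 |
| 0.30 / 0.33 | 20% / 20% | 28 | 42.0 / 46.2 |

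Equal stopping keeps the order right, and late stopping shifts it little. Unequal, early stopping can reverse it: in the fifth row arm B has the higher daily use and the lower count. The SAP restricts the count to users. At these rates that makes no practical difference, since 1 − 0.7^28 rounds to 1.000.

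**4. Any use.** With a constant daily probability, P(any use) = 1 − (1 − p)^n. At p = 0.02 this is 43.2% over 28 days and 96.6% over 168 days. With stoppers observed 28 days:

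- 10% stopping: 0.9 × 96.6% + 0.1 × 43.2% = 91.3%.
- 30% stopping: 0.7 × 96.6% + 0.3 × 43.2% = 80.6%.

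At p = 0.1 the corresponding figures are 99.5% and 98.4%. With strong variation between patients (beta-distributed p, mean 0.2, a + b = 1), any use is 56.0% over 28 days and 69.2% over 168 days. The arm figures are then 0.9 × 69.2% + 0.1 × 56.0% = 67.9% and 0.7 × 69.2% + 0.3 × 56.0% = 65.2%. The effect on any use runs from about 1 to 11 percentage points across these assumptions.

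**5. With a denominator.** In step 2, 62.16/155.4 = 0.40 and 57.12/142.8 = 0.40. In the fifth row, 46.2/154 = 0.30 and 41.58/126 = 0.33. The rate recovers daily use in each arm and restores the order.

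**The case against.** The strongest reply is that the SAP already has a measure of the right kind. Weekly mg is divided by diary entries, so a reader who infers that rescue is reported only in unadjusted form would be wrong. That stands, and it limits the point to two of three endpoints. The weekly measure does not repair the other two: it describes amount, it is limited to users, and a patient who has stopped the diary contributes no later weeks.

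Other replies also have force:

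- **Before versus on treatment.** A reader might set the pre-treatment any-use percentage (7 to 10 diary days) beside the on-treatment one (up to 168 days). At 2% per day these would be 13–18% and 97%. But no such comparison is planned, the washout is the same for all arms, and the day count is for the On-Treatment Period only.
- **Ceiling.** It is tempting to say that any use will be near 100% in every arm. That needs a shared, constant daily probability; with variation between patients the figure above is 69%.
- **Window.** The 28 to 168 days are nominal. Protocol 7.1 counts the oral drug as study drug, so the period can run longer for a patient who continues capsules, although diary reporting ends at week 24.
- **Prohibited NSAIDs.** The SAP 5.4 count may look like the same flaw. It is weaker: it runs through follow-up, patients who stop drug are asked to keep attending, and ending the count at arthropathy gives a coherent pre-event quantity.
- **Context.** Kaplan-Meier time to discontinuation (SAP 5.5.2) and exposure duration (SAP 5.6.2) will show unequal observation. They alert the reader but do not correct the rescue figures.

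**Conclusion.** The point holds in limited form. Any use and the number of rescue days lack an observation-time denominator, and the On-Treatment Period shortens with early stopping, so arms with unequal stopping are not directly comparable on these two measures. Under the assumed inputs the distortion in the day count is about 5 days in roughly 60. It runs from none (equal stopping) or under 2 days (late stopping) to 8.4 days (10% versus 30% stopping, with stoppers observed 28 days). The direction follows from the definitions; the size rests on daily-use and stopping rates that the documents do not give.

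It would go too far to say that the figures reflect observation time instead of rescue need: they reflect both. The summaries are descriptive and exploratory and lie outside the hierarchy in SAP 5.7.4, so the severity is minor.

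**What to change.** In SAP 5.7.5:

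- Report, per patient, rescue days divided by completed diary days in the On-Treatment Period, summarised by arm beside or in place of the raw count.
- Report the same rate for the 7 days before first dose. This also ties the pre-treatment figure to diary data; the SAP's Pre-Treatment Period begins at consent, before the diary starts.
- If any use is kept, also show it by week among patients with diary entries that week, with a note that later weeks include only patients still in observation.

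Optionally, in SAP 5.4, show prohibited-NSAID days per 100 days observed, with observation truncated at arthropathy where the count is.

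The cost is SAP wording and a denominator in the programs; no new data are needed. The rate does not remove every effect of early stopping. If daily use changes over time, early stoppers contribute only early days, and the weekly proportions still condition on remaining in observation. The per-diary-day rate is the core change.
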